The melatonin will be administered rectally in a fluid, followed by plasma samples over the following 24 hours. The melatonin formulation applied for rectal administration will be a 2.5 ml fluid containing 25 mg of melatonin. The delivery of the fluid is to be performed via an enema. The subjects will be asked to defecate, if possible in the morning, prior to the administration of melatonin.

Study session 3: Intravesical administration

The melatonin/dimethyl sulfoxide (DMSO) aqueous solution will be administered intravesically, followed by plasma samples over the following 24 hours. The melatonin used in the study will be applied intravesically through a catheter at a dose of 25 mg in 50 ml of a solution of 50% (w/w) DMSO in water, the solution containing melatonin at a concentration of 0.5 mg/ml. The subjects will be asked not to consume fluids three hours prior to the start of the study day, and will be asked to void their bladder prior to administration of melatonin.

Study session 4: Vaginal administration

The vaginal suppository containing melatonin will be administered vaginally, followed by plasma samples over the following 24 hours. The melatonin used in the study will be applied at a dose of 25 mg in a suppository (Witepsol S58) vaginally, by the participant themselves.

Study session 5: Transdermal administration

The melatonin will be administered topically as 1 g of a 2.5% (w/w) melatonin cream over a skin area of 20 x 20 cm (400 cm²), followed by plasma samples over the following 48 hours. The dose of melatonin used in the study will thus be 25 mg. The participants will be asked to refrain from using any other creams or lotions one day prior to the study session, and for the following 48 hours.

Outcomes

The outcomes are identical for four of study sessions of the trial (intravenous, rectal, intravesical, and vaginal). The transdermal study session will have a follow-up of 48 hours rather than 24 hours. These differences are outlined below.

Primary outcome

Plasma concentration of melatonin at baseline, 0 min, 10 min, 20 min, 30 min, 40 min, 50 min, 1 hour, 2 hours, 3 hours, 4 hours, 6 hours, 8 hours, and 24 hours. Blood samples are drawn from a peripheral venous catheter within the first 8 hours, and the 24-hour samples will be taken as a single venipuncture. Each blood sample will have a volume of 6 ml, totaling 84 ml for each of the four first study sessions. For the blood samples drawn from a peripheral venous catheter, 4 ml of blood

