
will be drawn as “waste”, to ensure that the following 6 ml consist of undiluted blood, totaling another 52 ml of blood. In total, the subjects will have 136 ml of blood samples each study session.

For the transdermal study session, blood samples are drawn at baseline, 0 min, 30 min, 1 hour, 2 hours, 4 hours, 6 hours, 8 hours, 10 hours, 12 hours, 16 hours, 24 hours and 48 hours. Intervals are based on data from previous pharmacokinetic studies of transdermal melatonin [23]. Blood samples are drawn from a peripheral venous catheter within the first 16 hours, and the 24- and 48-hour samples will be sampled through a single venipuncture each. Each plasma sample will have a total volume of 6 ml, totaling 78 ml for the transdermal study session. For the blood samples drawn from a peripheral venous catheter, 4 ml of blood will be drawn as “waste”, to ensure that the following 6 ml consist of undiluted blood, totaling another 44 mL of blood. In total, the subjects will have 122 ml of blood drawn samples for the transdermal study session.

Plasma samples will be kept in a locked freezer (with a temperature-alarm) at the Department of Surgery, Herlev Hospital. The plasma concentration will be assessed by radioimmunoassay (RIA)-technique at Gastrolab, Herlev Hospital. RIA-technique is a validated method of determining melatonin in plasma that has been used for years [28]. A bio-bank will be created, containing solely the plasma samples from this study (see Data Management for further details). In the case report forms (CRF), the collection time of each sample will be noted. The plasma concentrations will be delivered to the investigator digitally from the laboratory, and will afterwards be noted in the through double entry CRF, by independently two investigators.

Secondary outcomes

Sedative effects and other adverse effects

A Karolinska sleepiness scale (KSS)-score will be performed at baseline and once every hour for 8 hours, as well as at 24 hours, and noted in the CRF. For the transdermal study session, the score will

be performed at every hour on the first day until 16 hours, as well as at 24 and 48 hours. The KSS is frequently used to evaluate subjective sleepiness. The scale has been validated against performance and EEG-variables [29].

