The 25 mg melatonin will be administered as 2.5 ml of a 10 mg/ml fluid, as an enema via a plastic tube with a stud with an opening. The fluid used will be a 20% w/w glycofurol and 40% w/w DMSO aqueous solution. The plastic stud on the enema will be inserted into the rectum, and the fluid will be administered as a bolus. The enema is then removed, and a clock is started to measure time from administration.

Study session 3: Intravesical administration

50 ml of melatonin 0.5 mg/ml solution in the 50% (w/w) DMSO/water solvent will be aspirated into a 50 ml syringe, totaling 25 mg melatonin. A Clean Intermittent Catheter (CIC) is inserted into the subject through the urethra, into the bladder, and the bladder of the subject will be emptied. Afterwards, the 50 ml syringe will be connected to the CIC, and the 50 ml solution will be administered into the subject at a rate of 25 ml/minute over 2 minutes. The catheter is then removed, and a clock is started to measure time from administration. Subjects will be required not to void their bladder until after the 1-hour blood sample has been collected.

Study session 4: Vaginal administration

The 25 mg of melatonin will be administered in a suppository, vaginally. The subjects will be handed a suppository, which they will themselves take out of the blister pack, and insert vaginally. As soon as the suppository is administered, a clock is started to measure time from administration.

Study session 5: Transdermal administration

The melatonin cream will be administered over a skin area of 20 x 20 cm. This area will be measured and outlined with a marker on the subject's chest, starting at the medial end of the left clavicle, horizontally towards the mid-axillary line, and vertically parallel to the sternum towards the stomach. Afterwards, 1g of melatonin cream will be measured on a scale, on a piece of non-stick paper by the investigator. The subject will then apply the melatonin cream over the 20 x 20 cm area. The subject will be wearing a glove and only use the fingertips in order to maximize the dose applied. After the melatonin cream has been adequately applied, a clock is started to measure time from administration.

Adverse reactions

Adverse reactions to melatonin

Melatonin is non-toxic in both physiological and pharmacological doses [35]. In mice, rabbits, cats, and dogs, melatonin doses of 800 mg/kg administered intravenously demonstrated no toxicity [36].

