The number of patients needed for this study is not based on a power calculation. We have decided that 8 subjects are needed to collect information of how the plasma concentrations develop over time. Because of the risk of dropouts, we have chosen to include a total of 10 subjects.

Data will be presented as either mean (SD) or median (IQR), unless stated otherwise.

Data will be analyzed using IBM SPSS Statistics for Windows version 22.0 (IBM Corp., Armonk, NY, USA) and Graph Pad Prism version 7.0 (Graph Pad Software Inc., La Jolla, CA, USA).

Time to maximal concentrations (t_{\max}) and maximal plasma concentrations (C_{\max}) will be assessed directly at the relevant time points. The pharmacokinetic variables: absorption constant (k_a), absorption half-life ($t_{1/2}$ absorption), elimination rate constant (k_e) and elimination half-life ($t_{1/2}$ elimination) will be estimated by “the method of residuals” [57]. Areas-under-the-curve (AUC) of plasma concentrations will be calculated by applying the trapezoidal rule [58]. $AUC_{0-\infty}$ will be estimated as $AUC_{0-8 \text{ hours}} + (C_{8 \text{ hours}}/k_e)$. Bioavailability (f) will be calculated as follows:

$$f = 100 \times \frac{AUC_{0-\infty} (\text{rectal, intravesical, vaginal or transdermal}) \times D_{iv}}{AUC_{0-\infty} (iv) \times D_{\text{rectal, intravesical, vaginal or transdermal}}}$$
 where D represents the dose

administered.

Data monitoring and management

This study will be conducted in compliance with the protocol, the ICH-GCP guidelines and the applicable regulatory requirements. The standard procedures for quality control and quality assurance are followed in compliance with the ICH-GCP guidelines, and investigator/sponsor allows direct access to data/documents for monitoring, auditing, and inspection from both the Danish Medicines Agency (Lægemiddelstyrelsen) and the Good Clinical Practice (GCP)-unit. The GCP-unit will monitor the study. Data will be stored electronically on a secure server until 10 years

after the end of the study, after which all person-sensitive data are deleted. Blood samples will be destroyed after analysis, at a maximum of one year after sampling. A biobank will be created, solely containing these blood samples. Until analysis, the blood samples are kept in a locked freezer at -80°C (with a temperature-alarm) in a locked room at Gastroenheden D, Herlev Hospital. The blood samples will be analyzed with the RIA-technique at Gaslab, Herlev Hospital.

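### Intravesical dwell has only a 1-hour minimum and no provision to record the void, yet F and ka are computed as if absorption ran on undisturbed

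*Combined protocol and SAP*

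**What the plan says.** Administration, Study session 3, describes the instillation: "50 ml of melatonin 0.5 mg/ml solution in the 50% (w/w) DMSO/water solvent" is given through a catheter, "administered into the subject at a rate of 25 ml/minute over 2 minutes". The bladder is emptied first. Time zero follows: "The catheter is then removed, and a clock is started to measure time from administration". The one rule on what happens next is: "Subjects will be required not to void their bladder until after the 1-hour blood sample has been collected". No latest void time, scheduled void or drainage is given.

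On recording, the Primary outcome section says: "In the case report forms (CRF), the collection time of each sample will be noted". Other recorded items named in the protocol are sleepiness scores, adverse reactions and events, demographics and reasons for withdrawal. Void time, voided volume and urinary melatonin are not mentioned.

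The Statistics section estimates four quantities by the method of residuals, in a list that begins "The pharmacokinetic variables: absorption constant (k_a), absorption half-life" and goes on to the elimination constant and half-life. AUC to infinity is the trapezoidal AUC to 8 h plus the 8 h concentration divided by ke. F is the dose-adjusted ratio of this AUC to the intravenous one, with the administered dose as D. Nothing in the section refers to dwell.

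**The concern.** A bladder instillation is a depot that the subject can remove. Drug not absorbed by the first void is largely lost, so the fraction absorbed is a function of dwell time. The 1-hour hold equalises dwell up to that point only. After it, each subject may void when she chooses.

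Two results are exposed. F becomes an average over dwell times that the report could not state, and part of its between-subject spread would be voiding behaviour. The method of residuals assumes one uninterrupted first-order input. Emptying the bladder truncates that input and moves the back-extrapolated terminal line on which every residual depends.

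The stakes are modest but real. The protocol says no earlier pharmacokinetic study of this route exists, and it presents the results as needed before radioprotection trials. Only eight completers are required, so a few early or late voids can move the summary. An unrecorded void time cannot be recovered afterwards.

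**Working it through.** **Inputs from the protocol.** Dose: 50 ml × 0.5 mg/ml = 25 mg; 25 ml/min × 2 min = 50 ml, so the figures agree. Minimum dwell: 1 h. Sampling starts "Plasma concentration of melatonin at baseline, 0 min, 10 min, 20 min, 30 min, 40 min, 50 min, 1 hour, 2 hours, 3 hours" and goes on to 4, 6, 8 and 24 h. The protocol states no dwell-related figure to reproduce.

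**Assumptions (not in the documents).** Absorption half-life 10 min to 4 h; first void at T = 1 to 4 h; elimination half-life 0.75 h for the ka check, so ke = 0.693/0.75 = 0.924 per h; one compartment; no urinary dilution.

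**Step 1: fraction absorbed.** With a first-order depot emptied at T, the fraction is 1 − exp(−ka·T), where ka = 0.693/half-life.

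| Absorption half-life | T = 1 h | T = 4 h | Ratio |
|---|---|---|---|
| 10 min | 98.4% | 100% | 1.02 |
| 30 min | 75.0% | 99.6% | 1.33 |
| 1 h | 50.0% | 93.8% | 1.88 |
| 2 h | 29.3% | 75.0% | 2.56 |
| 4 h | 15.9% | 50.0% | 3.14 |

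For voids at 2 h against 1 h, the two slowest rows give only 50.0/29.3 = 1.7 and 29.3/15.9 = 1.8.

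**Step 2: does the planned AUC formula carry this into F?** Yes. On noise-free curves at the protocol's times (ka 0.5 per h), it gives F of 41%, 65% and 89% for voids at 1, 2 and 4 h, against exact fractions of 39.3%, 63.2% and 86.5%.

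**Step 3: added between-subject spread.** CV in F from dwell alone, by assumed ka:

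| Void times (uniform) | 0.1/h | 0.25/h | 0.5/h | 1/h | 2/h |
|---|---|---|---|---|---|
| 1–4 h | 31% | 26% | 20% | 11% | 3% |
| 1–2 h | 18% | 16% | 13% | 9% | 4% |

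**Step 4: ka by residuals.** After a void at T the curve declines with ke. In units of dose/volume, its back-extrapolated intercept is ka/(ka − ke) × [1 − exp(−(ka − ke)T)], which contains T. For ka 0.5 and ke 0.924, ka − ke = −0.424. The intercept is −1.18 × (1 − 1.53) = 0.62 at T = 1 h and −1.18 × (1 − 5.46) = 5.3 at T = 4 h. With the terminal line through 4, 6 and 8 h and residuals at 10–40 min, noise-free data return:

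| True ka (per h) | T = 1 h | 2 h | 3 h | 4 h |
|---|---|---|---|---|
| 0.5 | 2.54 | 1.37 | 1.14 | 1.04 |
| 2 | 3.34 | 2.24 | 2.07 | 2.02 |
| 4 | 4.72 | 4.03 | 4.00 | 4.00 |

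At true ka 0.5, void time alone moves the answer 2.54/1.04 = 2.4-fold. The error left at long dwell has another cause: elimination is then faster than absorption, and even with no void the method returns 1.09. Void time explains the movement along the row, not the whole distance from 0.5.

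**Step 5: what identifies ka before the void?** The six samples from 10 to 60 min precede every void. With 10% error and only ke fixed, a true ka of 0.35 per h (half-life 2 h) is estimated with a 5th to 95th percentile range of about 0 to 0.8. Fixing the intravenous volume as well narrows this to about 0.32 to 0.37. Noise-free Wagner-Nelson estimates from samples to 1 h return 0.17, 0.35, 0.50, 0.99 and 1.97 for true values of 0.17, 0.35, 0.5, 1 and 2, whatever the void time.

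**The case against.** The best reply is that the effect may be small. If absorption is nearly complete within the hour, the ratio is 1.02 and the residuals method returns 4.0 to 4.7 for a true 4 per h. If everyone voids within 1–2 h, the added CV is at most 18%. Urine also dilutes the 50 ml depot: at an assumed 60 ml/h, the ratios of 2.6 and 3.1 fall to 2.0 and 2.1 with a constant absorbing surface, or to 2.4 and 2.8 if the surface grows with volume. All of this stands. A reader might infer that F will differ two- to threefold between subjects; the documents do not support that, because they give neither an absorption rate nor void times.

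A reader might also infer that void time will certainly go unrecorded. The CRF is not among the documents, so one can say only that the protocol makes no provision for recording it.

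It can further be said that the primary outcome is plasma concentration, that F and ka are descriptive results in a study without a power calculation, and that one route is affected. F could be read as applying to a dwell of at least 1 h followed by free voiding. So it would be too strong to call intravesical F unusable. Even so, without void times nobody could tell fast absorption from an early void.

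Finally, samples up to 1 h share the same dwell and are not themselves disturbed. That is right: the fault in ka comes through the terminal line.

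**Conclusion.** The point holds as a gap in recording and analysis. Followed as written, the plan yields an intravesical F tied to a dwell time the report may be unable to state, and a ka that changes with when the bladder was emptied. The size cannot be fixed from the documents. For a 4 h against a 1 h void, F changes between 1.02-fold and 3.1-fold over assumed absorption half-lives of 10 min to 4 h, before dilution. The ka shift ranges from slight at a true 4 per h to 2.4-fold at 0.5 per h, given an assumed elimination half-life of 0.75 h. These figures rest on a one-compartment, first-order model. The direction is secure wherever absorption is incomplete at the void. It is worth correcting because the information is cheap on the day and lost afterwards.

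**What to change.** Leave the voiding instruction as it is, and make three changes.

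1. Record the time and volume of the first void after instillation in the CRF. Volume helps judge dilution; without a urine melatonin concentration it does not give the amount left unabsorbed.
2. Report each subject's intravesical F beside her dwell time, and describe F as conditional on that dwell.
3. For this route, replace the method of residuals with an estimate of ka from pre-void samples, using the subject's own intravenous ke and volume of distribution, for example by Wagner-Nelson: fraction absorbed = volume × [C(t) + ke × AUC(0–t)]/dose, with ka from the slope of ln(1 − fraction) on time. Fixing ke alone is not enough. Volume of distribution must be added to the listed parameters.

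The cost is two CRF fields, a different ka method for one route, and reliance on the intravenous session's parameters, whose own error enters ka. The method also assumes that all instilled drug could be absorbed given unlimited dwell. No extra blood sampling is needed.

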The suppository will consist of a Witepsol S58 base, containing 25 mg of melatonin. The Witepsol S58 base contains hard fat, polyoxyethylene (25) cetyl stearyl ether and glyceryl ricinoleate [30]. The suppositories will be stored at room temperature. The melatonin will be packaged as single dose suppository in blister packs. The sizes of the blister packs are to be decided. An applicator will possibly be included. The suppositories will be produced and packaged by Glostrup Apotek, according to GMP-guidelines.

Melatonin cream

The cream for transdermal application will consist of 25 mg/g melatonin as well as 150 mg/g DMSO, in a cream base. The dose for each application will be 1 g, and the cream will be packaged in 30 g tubes. The tubes will be stored at room temperature. The cream will be produced and packaged by Glostrup Apotek, according to GMP-guidelines.

Administration

A dose of 25 mg melatonin for local administration has been chosen. This dosage was based on the smallest doses that have demonstrated radioprotective effects in animals [7, 31-33]. The dose has been scaled for humans, taking into account that the effect aimed to achieve should be local, rather than systemic. All administrations of melatonin to the healthy volunteers will be performed by an investigator, except for the vaginal suppository and transdermal cream which will be administered by the subjects themselves.

Study session 1: Intravenous administration

On the day of the study, the intravenous solution will be prepared by an investigator: Two ml of ethanol (99.9%) will be aspirated into a 50 ml syringe. Two ml ethanol will be mixed into a glass of 25 mg dry melatonin, and aspirated back into the 50 ml syringe. Another 23 ml of saline 0.9% will be aspirated into the syringe. The solution will contain 25 mg melatonin in a 4 ml ethanol/46 ml saline solution (1 mg/ml). This solution will then be administered as a bolus through a venous line at an infusion rate of 2.5 ml/minute over 10 minutes. This method for delivering intravenous melatonin has been used in a previous pharmacokinetic study investigating exogenous melatonin administration [5, 34].

Study session 2: Rectal administration

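### Transdermal bioavailability is divided by an administered dose, but only the dispensed gram of cream is weighed; weighing the residue on paper and glove is a cheap, minor improvement

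*Combined protocol and SAP*

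**What the plan says.** All references are to the combined protocol and SAP.

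- **Nominal dose.** Study course, Study session 5: "The melatonin will be administered topically as 1 g of a 2.5% (w/w) melatonin cream over a skin area of 20 x 20 cm", followed by "The dose of melatonin used in the study will thus be 25 mg". The Melatonin cream paragraph under Storage gives the same strength: "The cream for transdermal application will consist of 25 mg/g melatonin as well as 150 mg/g DMSO, in a cream base".
- **Procedure.** Administration, Study session 5: "1g of melatonin cream will be measured on a scale, on a piece of non-stick paper by the investigator". Next, "The subject will then apply the melatonin cream over the 20 x 20 cm area", with the precaution "The subject will be wearing a glove and only use the fingertips in order to maximize the dose applied". The step after that is the clock: "After the melatonin cream has been adequately applied, a clock is started to measure time from administration".
- **Formula.** Statistics calculates F as 100 times the ratio of extrapolated AUCs (local route over intravenous), multiplied by the ratio of doses (intravenous over local), "where D represents the dose" administered.

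No section describes re-weighing the paper or glove, recording an applied mass, or correcting D for residue.

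**The concern.** The formula asks for the dose administered, but the procedure fixes only the dose dispensed. Between the scale and the skin there is an open transfer by gloved fingertips over 400 cm², done by each subject herself. Whatever stays on the paper or glove is counted in D although it never reached the skin. A subject with more residue would also appear to absorb less.

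The figure has some weight. The background text states that transdermal bioavailability has not been studied before, so readers will have no earlier value to compare it with. More subjects would not remove a systematic shortfall. The residue also cannot be recovered once the paper and glove are thrown away, whereas an AUC can be recalculated from recorded concentrations.

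**Working it through.** **1. Reproduce the stated dose.** 1 g x 2.5% = 1,000 mg x 0.025 = 25 mg. With the strength in the Storage section, 1 g x 25 mg/g = 25 mg. The stated figure is reproduced exactly, but it describes the gram on the paper.

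**2. Effect of residue on F.** Let A be the amount absorbed (mg) and r the fraction of the cream left on paper and glove.

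- F per dispensed dose = 100 x A / 25
- F per applied dose = 100 x A / [25 x (1 - r)]
- Ratio, dispensed to applied = 1 - r

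The ratio needs no assumption about how skin absorption changes with dose. Reading A from AUCs assumes linear disposition, which the protocol's formula already does.

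**3. Size.** The documents give no r. The values below are assumptions, and the 10% for F per applied dose is only an illustration.

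| Assumed r | Applied dose, 25 x (1 - r) | F reported with D = 25 mg, if F per applied dose is 10% | Correction factor, 1/(1 - r) |
|---|---|---|---|
| 1% | 24.75 mg | 9.9% | 1.010 |
| 2% | 24.5 mg | 9.8% | 1.020 |
| 5% | 23.75 mg | 9.5% | 1.053 |
| 10% | 22.5 mg | 9.0% | 1.111 |
| 20% | 20.0 mg | 8.0% | 1.250 |

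**4. Spread.** Suppose two subjects absorb the same 10% of what reaches the skin, one with r = 1% and the other with r = 20%. Their reported F values would be 9.9% and 8.0%, a ratio of 0.80/0.99 = 0.81, with no difference in absorption. If r is the same in everyone, the spread relative to the mean does not change.

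**5. Other inputs to the same formula.** Two separate matters bear on the net error.

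- *Intravenous dose.* Study course, Study session 1 describes 2 ml ethanol plus 23 ml saline, 25 ml in all. Administration, Study session 1 describes a 4 ml/46 ml solution, 50 ml in all, yet gives 1 mg/ml. At 2.5 ml/min for 10 min, 25 ml is infused. That is 25 mg if the volume is 25 ml. If it is 50 ml, it is 25 mg x 25/50 = 12.5 mg, and F calculated with an intravenous dose of 25 mg would be too high by 25/12.5 = 2.0. These passages must be reconciled.
- *AUC.* Statistics extrapolates from the 8-hour concentration, although transdermal samples run to 48 hours.

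**The case against.** The case on the other side is substantial.

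- **The quoted sentence describes a precaution.** Non-stick paper, a gram weighed for each subject, a glove and fingertip-only use all limit loss. A reader might infer that the protocol admits a material loss. It does not: it shows that loss was considered, and r of 1% or 2% is compatible with the text. This stands.
- **Nominal D is inferred.** The formula says dose administered, not 25 mg. That nothing is re-weighed is silence, and neither the CRF nor any working instructions are among the documents. This stands, though 25 mg is the only transdermal value the documents supply.
- **F per dispensed gram is a coherent quantity.** Under that definition residue is part of delivery and not an error. This stands. The protocol does not say that it means this, and its definition of D points the other way.
- **Other routes also use labelled doses.** Nothing measures what stays in the enema, in the catheter, or in the glass and line of the intravenous preparation. An intravenous loss would push F upwards. This stands in part. The cream differs in being spread by hand from an open sheet by the subject, and in being easy to weigh.
- **Reach is limited.** The primary outcome is plasma concentration. Under linear kinetics, tmax and the half-lives do not depend on r, and no test or decision threshold uses transdermal F. This stands and keeps the point minor.

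**Conclusion.** The point holds as a minor, cheap improvement. With D set to the dispensed 25 mg, F per applied dose is understated by the relative fraction r. Taken alone, this error can only be downward or zero, and variation in r between subjects adds to the spread of F. On the assumed range of 1% to 20%, the understatement is 1% to 20% (relative). That range is an assumption, and the precautions in the procedure favour a small r.

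A reader might go further and conclude that the reported transdermal F will be too low. The documents do not support that. The intravenous dose alone could move F upwards by a factor of up to 2.0, depending on how the conflicting volumes are reconciled, and the 8-hour cut-off is a further unresolved input. The net direction is therefore not established.

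The conclusion rests on two readings: that the protocol's silence means no re-weighing, and that F is meant per dose reaching the skin.

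**What to change.** Before the transdermal session, which comes last in the fixed order:

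1. Weigh the paper with its cream plus the unworn glove before application, and the paper plus glove immediately after it. The difference is the net mass applied.
2. Record the net mass in the CRF.
3. Report F with D(transdermal) = 25 mg/g x net mass applied (g), and also F per dispensed 25 mg. Label each, so that either definition can be read from the results.

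**Cost.** Two weighings and one CRF field per subject, on a scale that resolves about 10 mg. Dose, schedule and sampling do not change.

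**Downside.** 10 mg is 10/1,000 = 1% of the gram, so a residue near 1% would be at the limit of resolution, but the weighings would then show that residue is negligible. Moisture gained by the glove makes the applied mass look too small, and evaporation from the residue makes it look too large. Weighing at once keeps both errors small.
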